4.4 General Concomitant Medication and Supportive Care Guidelines

There is no restriction towards the use of any non-chemotherapeutic agent during administration of RT as specified for the symptom management.

A proton pump inhibitor is recommended one week prior and for three months following RT. Ondansetron 8 mg will be administered prior to each radiation treatment. It is optional for patients to receive corticosteroid premedication (e.g. dexamethasone 4 mg p.o. in a single dose) 15-60 minutes prior to each of three treatments. Analgesic premedication to avoid general discomfort during long radiation planning or treatment durations is also recommended when appropriate. Antiemetics will be ordered at the discretion of the attending physician. Mucositis/esophagitis may be treated with sucralfate or a GI cocktail (e.g. Tylenol #3 suspension, benadryl elixir, Maalox, viscous lidocaine). Intravenous hydration is recommended in patients with inadequate oral intake. Treatment-related diarrhea may be managed with loperamide. The recommended dose of loperamide is 4 mg initially (two capsules) then 2 mg after each loose stool, not to exceed 16 mg daily.

Administration of chemotherapy concurrent with RT is not allowed.

Chemotherapeutic agents given before or after RT are at the discretion of the treating physician, with exclusion of bevacizumab or vascular endothelial growth factor inhibitor, given concern for RT-related wound healing issues particularly regarding small bowel.

4.5 Duration of Therapy

Duration of SBRT is to occur within a 10 day time period. Completion of the three fractions of RT will be delayed or foregone if:

- Intercurrent illness that prevents further administration of treatment,
- Further treatment is felt to be likely to result in severe and permanent impairment, or death (life-threatening toxicity),
- The patient decides to withdraw from the study, or
- General or specific changes in the patient's condition render the patient unacceptable for further treatment in the judgment of the investigator.

The use of chemotherapy after RT will be at the discretion of the treating physician.

4.6 Duration of Follow Up

Patients will be followed on protocol for 12 months after initiation of RT or until death, whichever occurs first. Patients removed from protocol therapy for unacceptable adverse events will be followed until resolution or stabilization of the adverse event.

4.7 Criteria for Removal from Study

Patients will be removed from study (but followed for potential of toxicity) when any of the criteria listed in Section 4.4 applies. The reason for study removal and the date the patient was removed must be documented in the Case Report Form.

5. Radiation Therapy Guidelines

5.1 Treatment Related Planning Procedures

- 5.1.1. All patients will be evaluated prior to simulation for placement of fiducial markers (by endoscopic approach or interventional radiology) in or around the primary tumor, for purposes of stereotactic localization prior to SBRT. Marker placement is preferred but not required.
- 5.1.2. When done, the ideal timing of MRI will be ≥ 2 days after placement of fiducial markers.
- 5.1.3. All patients will undergo CT simulation ≥ 2 days after placement of markers, and prior to the first treatment using appropriate immobilization. Patients should have no food 2 hours prior to undergoing simulation. However, medications may be taken with liquid.
- 5.1.4. Patients will be positioned in a stable position capable of allowing accurate reproducibility of the target position from treatment to treatment.
- 5.1.5. Simulation with respiratory gating and acquisition of a 4D CT scan for retrospective respiration phase-based imaged sorting is highly preferred but not required.

5.2 RT Planning Parameters

- 5.2.1. The definition of volumes will be in accordance with the ICRU Report 62: Prescribing, Recording and Reporting Photon Beam Therapy. (ICRU, 1999)
- 5.2.1.1. A gross tumor volume (GTV) will be entered for each lesion, based on available imaging data.
- 5.2.1.2. In the absence of respiratory gating, an internal target volume (ITV) will be defined as the volume that accounts for intrafraction target motion.
- 5.2.1.3. A clinical target volume (CTV) will be defined as the GTV or ITV (when available) plus a margin for microscopic extension.
- 5.2.1.4. A planning target volume (PTV) will be determined which will correspond to CTV plus appropriate margin for tumor motion and set-up uncertainty.
- 5.2.2. 3D coplanar or non-coplanar beam arrangements will be custom designed for each case to deliver highly conformal prescription dose distributions. The treatment plan used for each patient will be based on an analysis of the volumetric dose, including dose volume histogram of the PTV and normal structures. 3D “forward” planning or “inverse” planning with beamlet intensity modulated treatment planning are allowed.
- 5.2.3. Treatment is to be delivered using a linear accelerator and photon energies ≥ 6 MV.
- 5.2.4. Corrections will be made to account for tissue heterogeneity.
- 5.2.5. RT is to be delivered to each site in 3 fractions over a period of up to 10 total days.
- 5.2.6. RT Dose: A phase I escalation of doses will be performed in order to determine in MTD in Gy. Doses of radiation will start at Level 1 and increase as follows in order to determine the MTD in Gy:
 - Level 1: 10 Gy/ fraction \times 3 fractions = 30 Gy

Level 2: 12.5 Gy/fraction x 3 fractions = 37.5 Gy

Level 3: 15 Gy/fraction x 3 fractions = 45 Gy

If DLT is met at Level 1, dose will be de-escalated to Level -1: 7.5 Gy x 3 fractions = 22.5 Gy

5.2.7. Doses will be prescribed to the PTV. The PTV may be covered by a lower isodose line than usually used in conventional radiotherapy planning, typically around 80% but ranging from 60-100%. Ideally, the prescription dose will cover >90% of the GTV (V100 GTV > 90%, and V95PTV > 90%). A lower coverage goal (with no minimum requirement of PTV coverage) will be acceptable if necessary to meet normal tissue constraints, which will be assigned priority over tumor coverage.

5.2.7.1. Any dose > 110% must be within the PTV.

5.2.8. Dose/volume constraints: The following table lists maximum dose limits to a point or volume within several critical organs. These are absolute limits, and are listed as total over 3 fractions and per fraction. In order to verify each of these limits, the organs must be contoured such that appropriate dose volume histograms

Organ	Volume	Dose
Spinal cord	Any point	21 Gy (7 Gy per fraction)
Esophagus	Any point	27 Gy (9 Gy per fraction)
Stomach	<2 cc	24 Gy (8 Gy per fraction)
	Any point	30 Gy (10 Gy per fraction)
Heart/pericardium	Any point	30 Gy (10 Gy per fraction)
Liver	700 cc	17 Gy (5.66 Gy per fraction)
Duodenum	<2 cc	24 Gy (8 Gy per fraction)
	Any point	30 Gy (10 Gy per fraction)
Jejunum/ileum	<2 cc	24 Gy (8 Gy per fraction)
	Any point	30 Gy (10 Gy per fraction)
Total kidney	200 cc	15 Gy (5 Gy per fraction)
Skin	Any point	24 Gy (8 Gy per fraction)

(DVHs) can be generated.

5.2.9. Contouring of normal tissue structures

- Spinal cord. The spinal cord will be contoured based on the bony limits of the spinal canal. The spinal cord should be contoured starting at least 10 cm above the superior extent of the PTV and continuing on every CT slice to at least 10 cm below the inferior extent of the PTV.
- Esophagus. The esophagus will be contoured using mediastinal windowing on CT to correspond to the mucosal, submucosa, and all muscular layers out to the fatty adventitia. The esophagus should be contoured starting at least 10 cm above the superior extent of the PTV and continuing on every CT slice to at least 10 cm below the inferior extent of the PTV.
- Stomach. The outer wall of the stomach will be contoured to include the cardia of the stomach to the pylorus.
- Heart/pericardium. The heart will be contoured along with the pericardial sac. The superior aspect (or base) for purposes of contouring will begin at the level of the inferior aspect of the aortic arch (aortopulmonary window) and extend inferiorly to the apex of the heart.

- Liver. The normal liver is defined as that portion of liver not radiographically involved by gross tumor (Normal liver volume minus GTV).
- Duodenum. The outer wall of the duodenum will be contoured from the edge of the pylorus of the stomach to the start of the jejunum, and include four segments of the duodenum.
- Jejunum/ileum. The jejunum and ileum will be contoured to include the outer wall of the small bowel distal to the duodenum to the end of the ileum, and also include the mesentery and vessels anterior to the aorta.
- Total kidney. Kidneys will be contoured to include the renal capsule and parenchyma up to the hilum.
- Skin. The skin will be defined as the outer 0.3 cm of the body surface. As such it is a rind of uniform thickness (0.3 cm) which envelopes the entire body in the axial planes. The cranial and caudal surface of the superior and inferior limits of the planning CT should not be contoured as skin unless skin is actually present in these locations (e.g., the scalp on the top of the head).

5.3 RT Treatment

- 5.3.1. The first fraction of RT should occur no earlier than 2 weeks after administration of the last dose of chemotherapy.
- 5.3.2. Patients should have no food 2 hours prior to receiving treatment. However, medications may be taken with liquid.
- 5.3.2. Orthogonal portal films (imaging to visualize fiducial markers) or cone beam CT must be obtained and approved by the radiation oncologist prior to each treatment. Treatment will preferably be administered with respiratory gating.

6. ADVERSE EVENTS

Adverse event (AE) monitoring and reporting will be performed.

- Radiation side effects are limited to the area involved in the treatment field. Acute and late toxicity related to radiation therapy may include fatigue, nausea and vomiting, skin erythema, subcutaneous fibrosis, esophagitis, pericarditis, diarrhea, myelitis, damage to the small bowel (including stricture or obstruction, bleed, fistula formation, or perforation), liver dysfunction, kidney damage, and radiation enteritis.
- Acute toxicity including Grade 4 nausea, Grade 4 skin toxicity, and Grade 3 liver toxicity will be referred to as dose limiting toxicities (DLT).
- Late toxicity including any Grade 3+ GI toxicity (small bowel damage including stricture or obstruction, bleed, fistula formation, or perforation; liver damage including ascites but not including abnormal lab values only; pancreatitis, cholecystitis) will be considered a toxicity of interest.
- All life-threatening Grade 4 and all fatal toxicities (Grade 5) must be reported immediately and evaluated.

- Acute toxicity: Acute side effects are considered as occurring \leq 28 days from the start of radiation therapy. They will be documented using the NCI Common Terminology Criteria for Adverse Events (CTCAE) version 3.0 (A copy can be downloaded from <http://ctep.info.nih.gov>). The relevant sections are included in the appendix.
- Late toxicity: Late side effects are considered as occurring $>$ 28 days from the start of radiation therapy through a 12 month total evaluation period. They will also be documented using the NCI Common Terminology Criteria for Adverse Events (CTCAE) version 3.0. The relevant sections are included in the appendix.
- University of Chicago Reporting Guidelines
 - If the reaction requires reporting, the Research Nurse or MD reports the adverse reaction to the Cancer Clinical Trials Office (CCTO) at [contact] by the end of the business day when he/she becomes aware of the event. Events occurring after business hours will be reported to the CCTO by 12 pm (noon) the next business day.
 - The following information is required when calling in the event:
 - Caller's Name and Telephone Number
 - Patient Initials
 - Patient Medical Record Number
 - IRB Protocol Number
 - PI of Study
 - Attending Physician
 - Date of Event
 - Description of Event (including grade of the event and attribution of the event and if the event required hospitalization)
 - E-mail is sent to the research nurse, attending physician and PI of the study informing them that adverse reaction notification has been received.
 - The University of Chicago's IRB Serious Adverse Event Form must be sent to the CCTO within **5 calendar days of event occurrence**. The UC IRB Serious Adverse Event form is available on-line at: <http://ors.bsd.uchicago.edu/HS/newirbforms>. This form must be typed. Once the forms are completed, the original is forwarded to the study PI to review and sign. The signed report is delivered to the QA Coordinator. A weekly report of delinquent or pending documents will be forwarded to the applicable person who reported the event. All delinquent reporting (greater than 10 days from event occurrence) must include documentation of reason for delinquency and may require implementation of an action plan.
 - Once the appropriate AE documents have been received, the CCTO forwards these to the IRB. A copy will be forwarded to the appropriate Research Nurse.
- Data Safety and Monitoring

- Data Safety and Monitoring will occur at the weekly University of Chicago GI oncology phase I/II conference meetings, which are lead by senior level medical oncologists. At each meeting, all active studies will be reviewed for safety and progress toward completion. Toxicities and adverse events will be reviewed at each meeting and a Data Safety and Monitoring form will be completed for each protocol and signed by either the Principal Investigator, the Chairman of the Department or by his designate if the Chairman is not available.

7. STUDY CALENDAR

Baseline evaluations (including pain score, performance status, and medications) are to be conducted within 21 days prior to start of protocol therapy. Scans must be done within 28 days prior to the start of therapy. In the event that the patient's condition is deteriorating, laboratory evaluations should be repeated within 48 hours prior to initiation of therapy.

	Pre-treatment	Week 1 of RT	Week 2 of RT	Post-treatment
Inclusion/exclusion	X			
Informed consent	X			
Pathology confirming cancer	X			
History and physical	X	X	X	X ^f
Vital signs	X	X	X	X ^f
Performance status and pain score	X	X	X	X ^f
Documentation of current medicines	X	X	X	X ^f
CT or MRI of abdomen ^a	X			X ^a
Hematology ^b	X	X	X	X ^f
Chemistry ^c	X	X	X	X ^f
β-HCG ^d	X			
Patient QOL Questionnaire	X			X ^f
Toxicity assessment ^e		X ^e	X ^e	X ^f

a = Imaging will be done within 28 days of RT start, and in follow up at 3-5 weeks after completion of RT.

Further abdominal imaging will be performed every 6 months for the first year after RT.

b = CBC with differential, platelet count

c = comprehensive metabolic profile (glucose, sodium, potassium, chloride, carbon dioxide, BUN, creatinine, calcium, total bilirubin, alkaline phosphatase, AST, ALT). CA19-9 will be measured at months 1, 6, 12 from the start of radiation therapy, then every 6 months indefinitely (off protocol).

d = for women of child bearing potential, serum beta-hCG

e = prior to each radiation treatment after the first fraction, and with all other post-treatment clinic visits

f = From the start of radiation therapy, visits will be q2 weeks for the first month; then at months 2, 4, 6, 9, and 12; then every 6 months indefinitely (off protocol).

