1.2. Secondary Objectives

Secondary objectives include defining toxicities, effect on pain score, and quality of life, the rate of post-treatment resectability, and local control (as measured by CT or MRI and defined as lack of progressive disease by RECIST criteria).

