the setting of unresectable pancreatic cancer, there are two published experiences using SBRT techniques (Hoyer, 2005; Koong, 2004). The experience from Stanford (Koong, 2004) with 15-25 Gy in one fraction has been favorable, with only 5 of 15 patients treated on this dose escalation protocol demonstrating grade 1-2 toxicity (nausea, diarrhea, abdominal pain) with no patient demonstrating grade 3+ toxicity on initial report. Meanwhile, all 6 patients treated to the highest dose of 25 Gy had local control of the disease. Longer term follow-up of 77 patients treated with 25 Gy demonstrated a local control rate of 84% at 1 year, with moderate late toxicity (Grade 2+) in 10 (13%) of patients (Chang, 2008). The nature of the toxicity was related to gastrointestinal function, including ulceration of the small bowel (n=3) or stomach (n=3), stricture of the duodenum (n=1) or biliary system (n=2), or perforation of the small bowel (n=1). Toxicity was increased for men who received prior external beam radiation therapy in addition to the single stereotactic dose of 25 Gy. The risk of severe toxicity (G3+) was approximately 10% in patients treated with SBRT alone. In contrast, a phase II study from Denmark (Hoyer, 2005) treated 22 patients with 45 Gy (15 Gy x 3 fractions) for unresectable pancreatic cancer and found lower rates of control. Local control was only 57% at 6 months. This lower rate of local control is consistent with the approximately 50% rates observed in other studies giving standard fractionation RT, including post-operative (Smeenk, 2007) and definitive settings (Moertel, 1981). Meanwhile, grade 2+ toxicity (defined in this study as performance status, nausea, diarrhea, or pain at day 14 assessment) was 79%. Of note, pretreatment evaluation revealed that patients had symptoms consistent with grade 2+ toxicity in approximately 63%, so the actual increase in toxicity over baseline is difficult to quantify given the grading schema used and the lack of follow-up past day 14. These discrepant reports of SBRT indicate a need for further trials to help identify the role of SBRT for unresectable pancreatic cancer. With the poor ability to achieve local control, it is of interest to note whether SBRT could be more effective than standard fractionation. Furthermore, as neither of these studies followed detailed gastrointestinal toxicity according to prospectively defined dosimetric planning criteria, it is important to better characterize the nature and frequency of such treatment.

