4.2 Measuring Health Related Quality of Life

Patient reported outcome measures will include the Functional Assessment of Cancer Therapy–Hepatobiliary (FACT-Hep) questionnaire, a 45-item self-reported instrument designed to measure health-related quality of life (HRQOL) in patients with hepatobiliary cancers including pancreatic cancers. The FACT-Hep consists of the 27-item FACT-G, which assesses generic HRQOL concerns including physical, emotional, social and functional well being, and the newly validated 18-item Hepatobiliary Subscale (HS), which assesses disease-specific issues (see Appendix D). The questionnaire will be administered to all patients on trial at baseline, post treatment at follow up exams at 1,2,4,6,9 and 12 months from the start of SBRT. The questionnaire will be completed in writing by the patients, and after 12 months from the start of radiation therapy it will not be required.

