4.3 Definition of Dose-Limiting Toxicity

The evaluation period of acute toxicity will be defined by the period of 28 days following the first fraction of RT. Dose Limiting Toxicity (DLT) will be defined according to Common Toxicity Criteria version 3.0 (See Appendix B) and includes the following acute toxicities:

- Grade 4 nausea (life-threatening consequences)
- Grade 4 skin toxicity (necrosis or ulceration of full thickness dermis, spontaneous bleeding from involved site)
- Grade 3+ liver toxicity including symptomatic ascites requiring invasive procedure, or total bilirubin $>3 \times$ ULN, or AST $>5 \times$ ULN, or ALT $>5 \times$ ULN that persists until day 28, and is attributable to radiation therapy.
- Grade 3+ enteritis (abdominal pain, fever, change in bowel habits with ileus, peritoneal signs) that is attributable to radiation therapy.

Patients must have a minimum of 3 weeks of follow-up after RT start for patient data to contribute enough follow-up for consideration of dose-limiting toxicity. However, any DLT that occurs with shorter follow-up will count towards the dose escalation rules. In addition, any grade 5 toxicity (i.e., death) considered possibly, probably or likely related to RT will be considered a DLT.

Any late toxicity that occurs beyond the 4 week period of evaluation will be closely followed and documented as a toxicity of interest. Included are the following severe late toxicities of RT:

- Grade 3+ gastrointestinal ulcer, fistula, stricture, or perforation (symptomatic and severely altered GI function, IV fluids or TPN ≥ 24 hrs, intervention indicated)
- Grade 3+ gastrointestinal mucositis (confluent ulcerations or pseudomembranes, bleeding with minor trauma)
- Grade 3+ gastrointestinal bleed (transfusion, interventional radiology or endoscopic or operative intervention)
- Grade 3+ gastrointestinal necrosis (inability to aliment adequately by GI tract, interventional radiology, intervention indicated)
- Grade 3+ liver toxicity including symptomatic ascites requiring invasive procedure, or total bilirubin $>3 \times$ ULN, or AST $>5 \times$ ULN, or ALT $>5 \times$ ULN, or asterixis, that is attributable to radiation therapy.

- Grade 3+ enteritis (abdominal pain, fever, change in bowel habits with ileus, peritoneal signs) that is attributable to radiation therapy.
- Grade 3+ pancreatitis (interventional radiology or operative intervention indicated)

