8.1.1 Definitions

Evaluable for toxicity. All patients will be evaluable for toxicity from the time of their first treatment with RT.

Evaluable for objective response. Only those patients who have measurable disease present at baseline and have had their disease re-evaluated will be considered evaluable for response. These patients will have their response classified according to the definitions stated below.

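### No toxicity grade is taken before the first fraction, so symptoms already present, mainly Grade 1-2, may be counted as SBRT toxicity

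*Combined protocol and SAP*

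**What the plan says.** Section 7 marks toxicity assessment in Week 1 of RT, Week 2 of RT and Post-treatment, but not under Pre-treatment. Footnote e gives the timing: "prior to each radiation treatment after the first fraction, and with all other post-treatment clinic visits". The first scheduled grade is therefore taken before fraction 2.

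Section 8.1.1 adds: "All patients will be evaluable for toxicity from the time of their first treatment with RT". Section 6 separates acute from late toxicity only by days since the start of radiation, with the cut at day 28.

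Other baseline data are collected. Section 7 states: "Baseline evaluations (including pain score, performance status, and medications) are to be conducted within 21 days prior to start of protocol therapy". The calendar also marks history and physical, vital signs, abdominal CT or MRI, hematology and chemistry before treatment. For FACT-Hep, Section 4.2 says: "The questionnaire will be administered to all patients on trial at baseline".

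The objective affected is in Section 1.2: "Secondary objectives include defining toxicities, effect on pain score, and quality of life".

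**The concern.** A toxicity table built from grades that begin after the first fraction cannot separate a symptom that started or worsened after SBRT from one that was already there. This population is likely to bring such symptoms. Section 2.1 lists pain, obstruction, bleeding and perforation as possible effects of the untreated disease. The Schema admits metastatic patients when local symptoms are present. Section 3.1.3 allows chemotherapy until 2 weeks before the first fraction.

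At stake is the descriptive toxicity profile. If symptoms present at entry are counted, the profile is biased upward by an amount that cannot be estimated afterwards. Complaints shared by the disease, chemotherapy and radiation are the most exposed: nausea, diarrhea and fatigue at Grade 1-2.

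**Working it through.** **1. Is a baseline grade supplied elsewhere?** Sections 4.3, 6 and 8.1.1 define events, time windows and evaluability, but ask for no grade before radiation. Section 9.3 covers resectability and local control and gives no analysis of toxicity. No worsening-from-baseline rule appears anywhere.

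**2. Can patients enter with a gradable abnormality?** Yes. Section 3.1.7 accepts total bilirubin up to 2.5 x ULN, and Appendix B grades >1.5 to 3.0 x ULN as Grade 2. For this laboratory item the starting grade can be recovered from baseline chemistry. For symptoms there is no such record.

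**3. Do the other baseline data fill the gap?**
- History and physical: no CTCAE grade is required.
- FACT-Hep: a patient-scored 0-4 scale over the past 7 days. It asks about nausea, diarrhea and fatigue, but the plan gives no conversion to CTCAE. No item names GI bleeding, obstruction or pancreatitis. It is not marked in either week of RT.
- Pain score, performance status, bilirubin, AST and ALT: a usable baseline exists.
- Timing: baseline evaluations may be 21 days before RT, and chemotherapy may end 14 days before it. The baseline visit can thus precede the last chemotherapy dose by up to 21 - 14 = 7 days. A grade just before fraction 1 would capture that effect.

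**4. How large can baseline symptoms be?** Section 2.2 gives, for the Danish study, Grade 2+ in about 63% before treatment and 79% at day 14.
- Difference: 79 - 63 = 16 percentage points.
- If everyone symptomatic before treatment was still symptomatic at day 14, the share of the day-14 figure already present was 63/79 = 0.80.
- With the smallest possible overlap, 63 + 79 - 100 = 42 points were present both times, and the share was 42/79 = 0.53.

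So between 16 and 79 - 42 = 37 points would be new. This assumes that the same patients were assessed at both times, which the protocol does not say. The range shows what a within-patient baseline grade adds: it replaces these bounds with a count.

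**5. Are the decision rules affected?** The plan's figures for the 18-patient rule reproduce by exact binomial: P(X >= 7 | n = 18, p = 0.50) = 0.881 (stated 0.88), and P(X <= 6 | n = 18, p = 0.25) = 0.861 (stated 0.86). Suppose unrelated Grade 3+ events at an assumed rate b were counted on top of a true 25%. Then p = 1 - 0.75 x (1 - b), and P(X >= 7) moves from 0.139 at b = 0 to 0.239 at b = 5%, 0.362 at b = 10% and 0.626 at b = 20%. The documents give no b. That shift would come from new disease events counted without an attribution test. A baseline grade would not remove them, so the change proposed here alters no stated figure.

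**The case against.** The strongest reply is that baseline status is well documented and only a number on a form is missing. History, pain score, performance status, laboratory values, imaging and FACT-Hep are all collected. A called-in event must carry "Description of Event (including grade of the event and attribution of the event and if the event required hospitalization". The liver DLT must be one "that persists until day 28, and is attributable to radiation therapy", and enteritis has the same attribution condition both as a DLT and as a late event. Most of this stands, and it rules out four stronger readings.

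- *Pre-existing symptoms will be reported as SBRT toxicity.* The documents support only that they may be, with no rule to prevent it. However, the attribution line in Section 6 applies to events that require reporting, not to the routine toxicity table.
- *The plan repeats the flaw it finds in the Danish study.* It does not. Section 2.2 says that study had a pre-treatment evaluation, and that "the actual increase in toxicity over baseline is difficult to quantify given the grading schema used and the lack of follow-up past day 14". This trial uses CTCAE v3.0 and 12 months of follow-up. What carries over is only that the increase over baseline is the quantity of interest.
- *The DLT and late-toxicity decisions are biased.* They are little exposed. Entry limits of 2.5 x ULN lie below the liver DLT thresholds of >3 x ULN (bilirubin) and >5 x ULN (AST or ALT). Pre-existing Grade 4 nausea is implausible with ECOG <= 2 and life expectancy above 3 months. Six of the eight late items lack attribution wording, but they are mostly discrete new Grade 3+ events, which a baseline grade would not sort.
- *The toxicity table would be mostly uninterpretable.* The Danish composite combined performance status, nausea, diarrhea and pain. Performance status and pain have a direct baseline here, so its 0.80 cannot be transferred.

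**Conclusion.** The point holds for the descriptive toxicity profile. As written, the calendar produces no CTCAE grade before the first fraction, and no rule handles symptoms already present. The likely effect is an upward bias in reported Grade 1-2 symptoms such as nausea, diarrhea and fatigue. Its size in this trial is unknown. The Danish figures show only that baseline symptoms can make up a large part of a raw rate in this disease, on a different composite.

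The conclusion assumes that some patients enter symptomatic, which the eligibility criteria allow, and that toxicity is tabulated from the scheduled assessments. It does not reach the MTD determination or the 18-patient rule. It is worth acting on because the correction is cheap and a grade not recorded at the time cannot be reliably reconstructed later.

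**What to change.** - Section 7: add an X for toxicity assessment under Pre-treatment.
- Footnote e: change the timing to before each fraction, including the first. Take the latest grade before the first fraction as the baseline.
- Coverage: grade the Appendix B terms by CTCAE v3.0, plus fatigue, vomiting and diarrhea, which Section 6 names as possible effects but Appendix B does not list.
- Section 9.3: state that each toxicity is reported both as worst grade and as worsening from the baseline grade.
- Leave the DLT and 7-of-18 rules as they are.

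Cost: a short form and a few minutes of grading per patient, at visits that already take place. No visit or procedure is added.
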